4.9.1.4 Derivation or calculation of genetic parameters

The number of patients who will agree to participate in the genetic research is unknown. It is therefore not possible to establish whether sufficient data will be collected to allow a formal statistical evaluation or whether only descriptive statistics will be generated. A statistical analysis plan will be prepared where appropriate.

5. DATA MANAGEMENT

5.1.15.1 Data collection methods and data validation at study site

5.1.1.15.1.1 Data flow

system is an electronic source data capturing and information management system. The system combines all aspects of source data capturing with process control and study management. All clinical and laboratory data, except those which are paper based, will be collected by the eSource system . Only paper-based data will be subject to data entry. For electronic data, no data entry will be performed. Data entered on paper CRF should be recorded legibly in blue or black ballpoint pen. Correction fluid or covering labels must not be used.

The responsible monitor will check data at the monitoring visits to the study site. The Investigator will ensure that the data collected are accurate, complete and legible. Data will be validated within the the data collected are accurate, complete and legible. Data will be validated within the the data collected are accurate, complete and legible. Data will be validated within the the data collected are accurate, complete and legible. Data will be validated within the the data collected are accurate, complete and legible. Data will be validated within the the data collected are accurate, complete and legible. Data will be validated within the the data collected are accurate, complete and legible. Data will be does being exported. Any changes made during validation will be documented with a full audit trail within the the data collected are accurate.

designs and builds a database in iVal to enter the paper-based data for adverse event and concomitant medication. The database and entry screens will be built and validated following a formal, documented verification plan and the system will be tested against the specification for the entry system. The setup will be controlled by test data entry. A standardised setup of SAS table sets in AstraZeneca specification will be done by the SAS programmer. Verification of the setup will be performed with dummy and test data.

The data manager will develop a DVS according to the protocol, the data dictionary of the iVal database for paper based-data and the description of the SAS table set for electronic data. Computerised checks to be performed on the data imported or entered into the databases will be defined in this document. The DVS will be sent to AstraZeneca or representative for review and approval.

Paper-based data will be sent to data management and entered into iVal. These data will be exported via the module iSAS later on and merged with the SAS tables in AstraZeneca format. The SAS table sets will be used for verification of the electronic study

--- **Formatted:** Bullets and Numbering

data following the specifications listed in the DVS. Only trained staff will have access to the databases. Every change will be fully audit-trailed.

The **data** files will be imported into SAS table sets. The imported data checked by the related verification programmes specified in the DVS. Data will be changed only in a controlled, audit-trailed, environment. After these data are considered as clean, they will be mapped into AstraZeneca data structure.

All study related electronic source data captured in **Data** Management after monitoring. These data will be imported into the SAS table set. Paper based data will be sent to Data Management after they have been monitored. **Data** Management reviews, logs and files them.

Any missing, impossible or inconsistent recordings will be referred back to the Investigator using a data query form and be documented for each individual subject before clean file status is declared.

In the case of genotypic data, only the date the subject gave consent to participation in the genetic research and the date the blood sample was taken from the subject will be recorded in

The genotypic data generated from the study will be stored in the AstraZeneca LIMS database or other appropriate system. This database is a secure database, which is separate the database used for the main study. Some or all of the dataset from the main study may be duplicated within the AstraZeneca LIMS database for exploratory genetic analysis

5.1.2 Study Data Management Plan (DMP)

The Study Data Management Plan (DMP) will describe the methods used to collect, check and process clinical data in detail. It will also clarify the roles and responsibilities for the different functions and personnel involved in the data management process. The DMP will also describe the data flow and timelines within the study.

5.1.3 Coding tools and dictionaries

Adverse events (AEs) and diagnoses from medical history will be classified according to the terminology of Medical Dictionary for Regulatory Activities (MedDRA). Concomitant medications will be classified according to the AZDD (AstraZeneca Drug Dictionary), the Anatomical Therapeutic Chemical (ATC) system and the Committee of Proprietary Medicinal Products (CPMP) route of administration dictionary. All coding will be performed by

5.2 Reporting of genotypic results

Results from any genetic research performed will be reported separately from the clinical study report. AstraZeneca will not provide individual genotype results to patients, their family members, any insurance company, an employer, clinical study investigator, general physician

or any other third party, unless required to do so by law. The patient's DNA will not be used for any purpose other than those described in the study protocol.

Individual patients will not be identified in any report or publication resulting from this work. The data and results of this study may be reviewed with collaborators and published, but neither the patient's name nor any other personal identifiers will appear in any publication or report.

6. STATISTICAL METHODS AND DETERMINATION OF SAMPLE SIZE

6.1 Statistical evaluation – general aspects

A comprehensive Statistical Analysis Plan (SAP) will be prepared before database lock and unblinding of the data in order to avoid any potential bias due to knowledge of the treatment received. It will detail analyses to be performed and summaries to be produced for the Clinical Study Report (CSR).

All statistical summaries and analyses will be performed by using SAS[®] (Statistical Analysis system, SAS-Institute, Cary NC, USA).

Pharmacokinetic parameters will be derived by non-compartmental analysis using WinNonLin Pro Version 5.0 or higher version.

6.2 Description of outcome variables in relation to objectives and hypotheses

This is an exploratory study and no hypotheses will be tested.

6.3 Description of analysis sets

The safety analysis set comprises all patients randomised into the study and receiving at least one dose of study medication. Patients will be analysed according to the treatment they actually received.

The PK analysis set is a subset of the safety analysis set and will only include patients who showed evaluable data from Day 1 and Day 14.

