In the multiple ascending dose part of the study the drug was given in doses of 30 mg, 70 mg and 120 mg once daily for 8 days. Twenty-seven subjects were randomised; 9 to placebo, and 6 to each of the dosing groups. No serious adverse events were reported; 47 non-serious adverse events were reported by 20 subjects. Again the majority of AEs were mild, 2 were moderate and one severe. The AEs considered to be moderate were headache (on 30 mg dose) and dyspepsia (on placebo). Severe AE was a headache on the 120 mg dose. Three subjects were withdrawn; one on the 30 mg dose because of asymptomatic nocturnal bradycardia, one on the 70 mg dose because of a run of premature atrial contractions, and one on the 120 mg dose because of headache, nausea and vomiting. The AEs on the 120 mg dose were deemed to be causally related to study drug. No significant laboratory or QT abnormalities were noted in this part of the study.

Overall, in this first administration to man study, AZD9668 was well tolerated except for the occurrence of headaches at the highest doses tested. The PK data from this study is detailed in Section 3.2.1.

Further details of the preclinical toxicology and pharmacology can be found in the Investigators Brochure.

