2. STUDY OBJECTIVES

2.1 Primary objective

The primary objectives of this study are

- 1. To investigate the tolerability of 14 days' dosing with AZD9668 in patients with COPD, as measured by vital signs, ECG, lung function, haematology, clinical chemistry, urinalysis and adverse event reporting.
- 2. To determine the plasma pharmacokinetics and renal clearance of AZD9668 in patients with COPD.

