3. STUDY PLAN AND PROCEDURES

3.1 Overall study design and flow chart

This Clinical Study Protocol has been subjected to a peer review according to AstraZeneca standard procedures.

This study is a randomised, double-blind, placebo-controlled, parallel-group, single-centre study to evaluate the tolerability and pharmacokinetics of AZD9668 administered for 14 days in patients with moderate to severe COPD (GOLD stages II and III). 18 patients will be randomly assigned to receive either AZD9668 or matching placebo orally (in a ratio of 2 active: 1 placebo). On Day 1 patients will receive a single morning dose of 60 mg of AZD9668 (or matching placebo) for single dose PK. This will be followed by daily doses of 60 mg bid (twice daily, 12 hours apart) on Days 2 to 13 and finally a single morning dose of 60 mg on Day 14 for steady state PK.

The study will consist of 5 visits.

Patients must provide full written informed consent before any study-related procedures, restrictions or screening assessments are carried out.

Visit 1: Screening visit (Day –21 to Day –8): At Visit 1, after having given written informed consent, patients will be enrolled into the study and screened for eligibility (Table 1). If eligibility is confirmed at Visit 1, patients will be issued with a BronkoTest[®] diary card (to be completed daily for the remainder of the study) and asked to return to the CPU at Visit 2.

Visit 2: Treatment Period (Day –1 to Day 3): The day before dosing is defined as Day –1 and the day of dosing as Day 1, Day 0 does not exist.

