4.5.1 Collection of biological samples

Blood samples (3 ml K₂EDTA) for determination of AZD9668 in plasma will be taken at the times presented in the detailed study plan (Table 1).

Blood samples will be collected, labelled and shipped as detailed in the laboratory handbook. The date and time of collection will be recorded.

Urine will be passed into a specially provided container at the times presented in Table 1. Urine samples will be collected, handled, labelled and shipped as detailed in laboratory handbook. The date and time of collection will be recorded.

Samples should be stored at -18° C or below, and analysed within the timeframe after collection for which the stability in the samples has been validated and found acceptable. Results from analyses stored longer than the period stated will not be reported.

Aliquots of sputum for AZD9668 analysis will be collected, handled, labelled and shipped as detailed in the laboratory handbook. The date and time of collection will be recorded.

Samples should be shipped to the appointed bioanalytical laboratory at pre-determined dates during the course of the study.

The methods used will be referred to in the clinical study report.

Samples will be disposed of within one month after the clinical study report has been finalised.

4.5.2 Drug concentration measurements, and derivation or calculation of pharmacokinetic parameters

Samples for determination of AZD9668 in plasma and urine will be analysed by

, on behalf of , AstraZeneca R&D , using validated methods of liquid chromatography and mass-spectrometry (LC-MS/MS). The lower limit of

quantification (LLOQ) of AZD9668 in plasma and urine will be 1.00 nM and 0.2 μ M, respectively.

The PK parameters will be calculated using non-compartmental analysis. The pharmacokinetic parameters will include:

Day 1: AUC_(0-t), AUC₍₀₋₂₄₎, AUC, t_{1/2}, CL/F, V_z/F, C₂₄, CL_R, A_e and F_e(%)

Day 7: Cmin,ss

Day 14: $C_{min,ss}$, $C_{max,ss}$, $t_{max,ss}$, $AUC_{(0-t),ss}$, $AUC_{(0-24),ss}$, $C_{24,ss}$, AUC_{ss} , $t_{1/2ss}$, CL/F_{ss} , V_z/F_s , R_{ac} , CL_R , $A_{e,ss}$ and $F_{e,ss}(\%)$

The accumulation ratio (R_{ac}) will be calculated using the following equation:

AUC(0-24),ss Day 14/AUC(0-24) Day 1.

An investigation of the AZD9668 concentrations in sputum will be conducted using a method of liquid chromatography and mass spectrometry (LC-MS/MS) based on that validated for human plasma.

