6.4 Method of statistical analysis

6.4.1 General analysis methods

Data will be summarised by treatment using descriptive statistics. All data (including derived data) will be listed, and will be summarised and plotted as appropriate, further details of the output to be produced will be contained in the SAP.

In addition biomarker data will be analysed using Analysis of variance The exploratory data may be explored further, and this information may be included in the CSR. Demographic and baseline variables (medical and surgical history details and abnormal results of physical examinations) will be summarised and listed.

The safety analysis set will be used as the primary analysis data set for the reporting of safety data; while the analysis of PK data will be based on the pharmacokinetic analysis set.

No imputation method for missing values will be used; data will be evaluated as observed.

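### The PK analysis set requires evaluable data on both Day 1 and Day 14, so patients who stop before Day 14 drop out of the Day 1 and Day 7 PK summaries

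*Protocol*

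**What the plan says.** Protocol Section 6.3 defines the PK analysis set as a subset of the safety set that "will only include patients who showed evaluable data from Day 1 and Day 14". Section 6.4.1 adds that "the analysis of PK data will be based on the pharmacokinetic analysis set". No other PK set is defined, and the term evaluable is not explained.

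PK is one of the two primary objectives: "To determine the plasma pharmacokinetics and renal clearance of AZD9668 in patients with COPD" (Section 2.1). Day 1 is a separate single-dose occasion, with one morning dose given "for single dose PK" (Section 3.1). Section 4.5.2 gives Day 1 its own parameters (AUC, half-life, CL/F, V_z/F, CL_R, A_e, F_e) and Day 7 a trough. The only listed parameter built from both days is R_ac, calculated as "AUC(0-24),ss Day 14/AUC(0-24) Day 1".

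On missing data, Section 6.4.1 says "No imputation method for missing values will be used; data will be evaluated as observed". It also says "All data (including derived data) will be listed".

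Under Section 3.3.5.2, patients who discontinue are asked, if possible, to undergo the Visit 5 procedures. Table 1 shows no PK sampling at that visit.

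**The concern.** Membership of the set depends on something that happens up to two weeks after the Day 1 profile is complete. A patient with a full Day 1 profile who stops on, say, Day 8 contributes to no Day 1 or Day 7 summary, although none of those parameters uses Day 14 data. This also sits badly with the rule that data are evaluated as observed.

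Two things are at stake. The first is information: there are only 12 active patients, and PK is a primary objective. The second is representativeness. The other primary objective is tolerability, so a patient who stops for an adverse event is one whose exposure a reader will want in the summary. If high exposure makes stopping more likely, the Day 1 geometric mean, CV and maximum will all tend to be too low. Section 3.2.1 puts the predicted margin to the AUC exposure limit at 1.4, so the upper end of the exposure range is of interest.

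**Working it through.** **Size of the active arm.** 18 patients randomised 2:1 gives 18 × 2/3 = 12 on AZD9668, which agrees with Section 3.2.1. Section 6.5 bases the number on feasibility, so there is no power calculation to reproduce.

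**What one excluded patient represents.** Section 3.1 schedules a pre-dose sample and 11 post-dose samples on Day 1, one sample on Day 7, and 12 again on Day 14. That is 12 + 1 + 12 = 25, which agrees with Table 3. A patient who stops between Day 7 and Day 14 has given 13 of the 25 plasma samples and three timed Day 1 urine collections. None of these enters a summary.

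**How often this could happen.** The protocol states no withdrawal rate, so the rate is an assumption. Section 1.1 gives one reference point, the volunteer multiple-dose part, with 27 subjects = 9 placebo + 3 × 6 active. It reports: "Three subjects were withdrawn; one on the 30 mg dose because of asymptomatic nocturnal bradycardia". The other two were on 70 mg (premature atrial contractions) and 120 mg (headache, nausea and vomiting). Only the events on 120 mg are described as causally related to study drug. This gives 3/18 for all withdrawals and 1/18 for the drug-related one.

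With withdrawal probability p and independent patients, the expected number left out is 12p, and P(at least one) = 1 − (1 − p)^12.

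| Assumed p | Expected number of 12 left out | P(at least one) |
|---|---|---|
| 5% | 0.6 | 0.46 |
| 1/18 | 0.67 | 1 − (17/18)^12 = 0.50 |
| 10% | 1.2 | 0.72 |
| 3/18 | 2.0 | 1 − (15/18)^12 = 0.89 |
| 25% | 3.0 | 0.97 |

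**Effect on the Day 1 summaries if two of 12 are left out.**

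- Stopping unrelated to exposure: there is no bias. The standard error of the mean log exposure rises by a factor √(12/10) = 1.095, about 10%.
- Worst case, the two highest exposures are the two lost: the between-patient CV is not given, so 20% to 50% is assumed, with log-scale SD s = √ln(1 + CV²). In 200,000 simulated sets of 12 log-normal exposures, removing the top two multiplied the geometric mean by 0.947 at CV 20% and by 0.878 at CV 50%, a fall of about 5% to 12%. An assumed CV of 40% appeared as about 31%.

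**Effect of changing the rule.** Day 1 would keep every active patient with an evaluable Day 1 profile, up to 12. R_ac would be unchanged. Day 14 could gain only patients who lack an evaluable Day 1 profile.

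**The case against.** The strongest defence has four parts.

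1. *Nothing is hidden.* All data are listed, so a reader can set an early stopper's Day 1 concentrations beside that patient's adverse events, which use the safety set. This stands: the loss is from the summaries and plots, not from the report. A reader might infer that the data are thrown away, and Section 6.4.1 does not support that.
2. *The set is not confined to patients who tolerated the drug.* A reader might infer that it is. Sections 3.2.1 and 3.4.2 allow a patient who does not tolerate the study dose to continue on a reduced one, and such a patient can reach Day 14 and stay in the set. Others can leave for reasons such as exacerbation or loss to follow-up (Section 3.3.5.1). This stands too. The selection is on reaching Day 14 with evaluable data.
3. *Exposure-related stopping is not shown.* The volunteer withdrawals were one at each dose level, and two were rhythm findings. Section 3.2.2 sees no reason to link events other than headache to the drug, and the entry criteria here exclude many patients with arrhythmia. This stands as a limit on the bias argument. It does not remove the possibility: headaches occurred consistently at high doses, and the total daily dose on Days 2 to 13 (120 mg) equals the top volunteer multiple dose.
4. *A common set lets single-dose and steady-state results refer to the same patients.* That is a legitimate aim, but it can be met by a paired comparison in patients evaluable on both days, without restricting the stand-alone Day 1 and Day 7 summaries.

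It might also be said that analysis-set detail belongs in the statistical analysis plan. Here, however, the protocol fixes a restrictive definition, which a plan that follows it would inherit.

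**Conclusion.** The point holds as a badly fixed analysis rule. Read literally, Sections 6.3 and 6.4.1 leave every patient without evaluable Day 14 data out of the Day 1 and Day 7 PK summaries, and nothing in the definition of those parameters calls for it.

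The certain cost is lost information from an arm of 12. Understatement of Day 1 exposure and its spread is a risk that depends on whether stopping is related to exposure. The 5% to 12% figure is a deliberate worst case with an assumed CV.

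The 0.89 probability should not be read as a forecast. It carries the volunteer rate of 3/18 over from a different population, regimen and duration, and the assumed rates of 5% to 25% give 0.46 to 0.97. Nor should the loss of precision be read as damage to a planned interval: Section 6.4.2 reports descriptive statistics without confidence intervals, and Section 6.2 tests no hypotheses. The change is worth making because PK is a primary objective and the correction is small.

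**What to change.** Replace the definition in Section 6.3 along these lines: the PK analysis set comprises all patients who received at least one dose of AZD9668 and have at least one evaluable PK parameter; each parameter is summarised over all patients evaluable for it on that day; evaluable data on both days are required only for R_ac and for any paired Day 1 versus Day 14 comparison.

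This needs no extra visit, sample or assay. The downside is that the number of patients will differ between parameters and days, so unpaired Day 1 and Day 14 summaries will not describe exactly the same patients. Section 6.4.2 already reports the number of observations for each parameter, so the difference will be visible.

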6.4 Method of statistical analysis

6.4.1 General analysis methods

Data will be summarised by treatment using descriptive statistics. All data (including derived data) will be listed, and will be summarised and plotted as appropriate, further details of the output to be produced will be contained in the SAP.

In addition biomarker data will be analysed using Analysis of variance The exploratory data may be explored further, and this information may be included in the CSR. Demographic and baseline variables (medical and surgical history details and abnormal results of physical examinations) will be summarised and listed.

The safety analysis set will be used as the primary analysis data set for the reporting of safety data; while the analysis of PK data will be based on the pharmacokinetic analysis set.

No imputation method for missing values will be used; data will be evaluated as observed.

6.4.2 Pharmacokinetic concentrations and variables

The pharmacokinetic analyses will be performed by or under the guidance of International GmbH.

For descriptive statistics of plasma concentrations

- if, at a given time point, 50% or less of the plasma concentrations are nonquantifiable (NQ), the geometric mean (gmean), CV, geometric mean ± SD, arithmetic mean and SD will be calculated by substituting the lower limit of quantification (LLOQ) for values which are NQ.
- if more than 50%, but not all, of the concentrations are NQ, the gmean, CV, gmean ± SD, arithmetic mean and SD will be reported as not calculable (NC)
- if all the concentrations are NQ, the geometric mean and arithmetic mean will be reported as NQ and the CV, gmean ± SD and SD as NC

If the calculation of the geometric mean - SD results in a value less than the LLOQ, NQ will be displayed.

Pharmacokinetic parameters will be calculated using non-compartmental analysis. Plasma concentrations of AZD9668 below the LLOQ at the end of the curve will not be considered for pharmacokinetic analysis, however if concentrations below the LLOQ between measurable concentrations should be set to LLOQ/2. All pre-dose samples which are below LLOQ will be set to zero. The actual sampling time will be used for the analysis. The maximum plasma concentration (C_{max}) and the time to reach the maximum plasma concentration (t_{max}) will be determined by visual inspection of the plasma concentration-time profile. The area under the plasma concentration-time curve from time zero to 24 h after dosing AUC(0-24) and from zero to the time of the last quantifiable plasma concentration (t_{last}) AUC_(0-t), will be calculated using the linear trapezoidal rule (linear/log interpolation). The rate constant of the slowest disposition phase (λ_z) will be calculated by log-linear regression of the terminal portion of the concentration-time profile where there were sufficient data (i.e. at least 3 time points and R^2 adjusted is greater than or equal to 0.9). If these criteria are not fulfilled, AUC, CL/F, $t_{1/2}$ and Vz/F will not be reported. The terminal half-life ($t^{1/2}$) will be derived from the equation $\ln(2)/2$ λ_z . The area under the plasma concentration-time curve from time zero to infinity (AUC) will be determined by using λ_z to extrapolate AUC_(0-t) to infinity (provided less than or equal to

20% of the AUC is extrapolated). Total apparent drug clearance (CL/F) and the terminal volume of distribution (V_z /F) will be estimated by dividing the dose by AUC, and product of λ_z and AUC, respectively. The equivalent PK parameters determined at steady state will also be calculated.

All pharmacokinetic parameters (except t_{max}) will be summarised by the number of observations, geometric mean, coefficient of variation (CV, calculated as 100 x v [exp (s²)-1], where s is the standard deviation of the data on a log scale), arithmetic mean, standard deviation (SD) using untransformed data, median, minimum and maximum. t_{max} will be summarised using median, minimum and maximum and number of observations.

For the urine data the amount of drug recovered for each individual collection period and the total amount over the collection period will be calculated. In addition the percentage of drug recovered for each collection period (and the total percentage recovered over the collection period) and the overall CL_R will be calculated. Summary statistics will be the same as for the plasma PK parameters.

Plasma concentration profiles will be presented graphically as individual curves and geometric mean plots, by study day, on both linear and log concentration scales.

